**Document History – Changes compared to previous final version of SAP**

Date	Time point	Reason for update	Outcome for update	Section and title impacted (Current)
06- Apr- 2021	Prior to DB First Patient First Visit	Creation of final version	N/A - First version	NA

13- Jan- 2023	Prior to DB lock of primary analysis	Creation of Amendment 1.0	Replaced ‘sequentially’ allocated with ‘randomly’ allocated in all instances	All sections
			Removed the note on cut-off date for primary analysis	Section 2.1
			Removed week 60 assessment and updated time interval for week 72 in table for molecular assessment	
			Added statement for mapping EOT assessment	
			Added week 72 for hematologic response assessment	
			[REDACTED]	
			Updated the criteria for generating TFLs for subgroup analysis	Section 2.2.1
			Replaced duration of exposure with non-zero dose with Time on treatment	Section 2.4.1
			Deleted cardiovascular risk factors not mentioned in Ecrf	Section 2.6.5.3
			Deleted section on liver function risk assessment as the data is not collected	
			Updated the secondary objectives to align with protocol	Section 2.8
			Updated the criteria to handle missing MMR rates	Section 2.8.3

15- Feb- 2024 Prior to DB lock Creation of  
of Interim  
analysis  
Amendment 2.0

Updated the change to  
protocol specified analysis

Section 4

Updated time windows for  
week 48 and 72 for  
molecular response

Section 2.1.1

## List of abbreviations

ABL	Abelson proto-oncogene
ADME	Absorption, Distribution, Metabolism, and Excretion
AE	Adverse Event
AESI	Adverse event of special interest
ALP	Alkaline phosphatase
ALT	Alanine aminotransferase/glutamic pyruvic transaminase/GPT
ANC	Absolute neutrophil count
AST	Aspartate aminotransferase/glutamic oxaloacetic transaminase/GOT
ATP	Adenosine triphosphate
AUC	Area under the curve
AV	block Atrioventricular block
b.i.d.	bis in die/twice a day
BC	Blast crisis
BCR	Breakpoint Cluster Region gene
BCR-ABL	BCR-ABL fusion gene (also called the Philadelphia chromosome)
BID	bis in diem/twice a day
BMI	Body Mass Index
CBC	Complete Blood Count
CDP	Clinical Development Plan
CDS	Core Data Sheet
CHR	Complete Hematological Response
CI	Confidence Interval
CK	Creatinine Kinase
[REDACTED]	[REDACTED]
CML	Chronic Myelogenous Leukemia
CML-AP	Chronic Myelogenous Leukemia-Accelerated Phase
CMO&PS	Chief Medical Office and Patient Safety
CO	Country Organization
CO2	carbon dioxide
[REDACTED]	[REDACTED]
CP	Chronic phase
CRF	Case Report/Record Form (paper or electronic)
CRO	Contract Research Organization
CSP	Clinical study protocol
CSR	Clinical study report
CTCAE	Common Terminology Criteria for Adverse Events
CV	Coefficient of variation

CYP3A4	Cytochrome P450 3A4
DBP	Diastolic Blood Pressure
DDI	Drug-drug interaction
DLCO	Carbon monoxide diffusing capacity
DLT	Dose Limiting Toxicity
DMC	Data Monitoring Committee
DNA	Deoxyribonucleic acid
DQF	Data Query Form
DS&E	Drug Safety and Epidemiology
DSMB	Data Safety Monitoring Board
DSUR	Development safety update report
ECG	Electrocardiogram
eCOA	Electronic Clinical Outcome Assessment
ECOG	Eastern Cooperative Oncology Group
eCRF	Electronic Case Report Form
EDC	Electronic data capture
ELISA	Enzyme-linked immunosorbent assay
ELN	European Leukemia Network
EOT	End of Treatment
eSAE	Electronic Serious Adverse Event
eSource	Electronic Source
EU	European Union
FAS	Full Analysis Set
FDA	Food and Drug Administration
FIH	First In Human
FSH	Follicle Stimulating Hormone
GCP	Good Clinical Practice
GCS	Global Clinical Supply
GDPR	General Data Protection Regulation
GFR	Glomerular Filtration Rate
GGT	Gamma-glutamyl transferase
H	Hour
hADME	Human ADME study (Absorption, Distribution, Metabolism and Excretion)
HBsAg	Hepatitis B surface antigen
HDL	High density lipoprotein
i.v.	Intravenous
IB	Investigator's Brochure
ICF	Informed Consent Form
ICH	International Council for Harmonization of Technical Requirements for Pharmaceuticals for Human Use
IEC	Independent Ethics Committee
INR	International normalized ratio
IWRS	Interactive Web Response System
IRB	Institutional Review Board

IRT	Interactive Response Technology that includes Interactive Voice Response System and
Km	Michaelis-Menten constant
K-M	Kaplan-Meyer
LDH	Lactate dehydrogenase
LDL	Low density lipoprotein
LFT	Liver function test
LLN	Lower limit of normal
LLOQ	lower limit of quantification
LSC	Leukemia stem cell
MCyR	Major Cytogenetic Response
mCyR	Minor Cytogenetic Response
[REDACTED]	[REDACTED]
MedDRA	Medical dictionary for regulatory activities
Mg	milligram(s)
mL	milliliter(s)
MMR	Major Molecular Response
MRI	Magnetic resonance imaging
NCDS	Novartis Clinical Data Standards
[REDACTED]	[REDACTED]
NOVDD	Novartis Data Dictionary
[REDACTED]	[REDACTED]
OS	Overall survival
p.o.	oral(ly)
[REDACTED]	[REDACTED]
PCR	Polymerase Chain Reaction
PCyR	Partial Cytogenetic Response
PD	Pharmacodynamic(s)
Ph+	Philadelphia chromosome positive
PHI	Protected Health Information
[REDACTED]	[REDACTED]
PLT	Platelets
PPD	Premature Participant Discontinuation
PPS	Per-protocol set
[REDACTED]	[REDACTED]
PSD	Premature Subject Discontinuation
PSUR	Periodic safety update report
PT	prothrombin time
QD	Quaque die/once a day
QMS	Quality Management System
QT	Q to T interval (ECG)
QTcF	QT interval corrected by Fridericia's formula
R Value	ALT/ALP x ULN
RAP	The Report and Analysis Plan
RBC	red blood cell(s)

RDC	Remote Data Capture
RDE	Recommended dose for expansion
REB	Research Ethics Board
RNA	Ribonucleic acid
RoW	Rest of World
RP2D	Recommended phase two dose
RQ-PCR	Real time quantitative polymerase chain reaction
s.c.	Subcutaneous
SAE	Serious Adverse Event
SAP	The Statistical Analysis Plan (SAP) is a regulatory document which provides evidence of preplanned analyses
SBP	Systolic Blood Pressure
SC	Steering committee
sCR	serum creatinine
SD	Standard deviation
SGOT	Serum glutamic oxaloacetic transaminase
SGPT	Serum glutamic pyruvic transaminase
SmPC	Summary of Product Characteristics
SOP	Standard Operating Procedure
SUSAR	Suspected Unexpected Serious Adverse Reaction
TBIL	Total bilirubin
TD	Study medication Discontinuation
TdP	Torsades de Pointes
TKI	Tyrosine Kinase Inhibitor
TTF	Time to treatment failure
UGT	Uridin diPhospho-glucuronosyltransferase
ULN	Upper limit of normal
ULQ	upper limit of quantification
US	United States
USPI	US prescribing information
UTI	Urinary Tract Infection
WBC	White blood cell(s)
WHO	World Health Organization
WoC	Withdrawal of Consent

## 1 Introduction

This statistical analysis plan (SAP) describes all planned analyses of primary objective, secondary objectives [REDACTED] for the clinical study reports (CSR) of study CABL001AUS04, a phase 3b, multi-center, open-label, study of oral asciminib monotherapy in patients with Chronic Myelogenous Leukemia in chronic phase (CML-CP), previously treated with at least 2 ATP-site tyrosine kinase inhibitors (TKI) (i.e. imatinib, nilotinib, bosutinib, dasatinib or ponatinib) in case of absence of T315I mutation or previously treated with at least 1 ATP-site tyrosine kinase inhibitors (i.e. imatinib, nilotinib, bosutinib, dasatinib or ponatinib) in case of presence of T315I mutation.

The main purpose of this document is to describe the statistical methodology that will be used for this clinical study.

The analysis described here will be conducted by Novartis using statistical software SAS® Version 9.4 or higher, according to the Statistical methods and data analysis Section 12 of the study protocol.

Unless otherwise specified, the statistical methodologies including the analysis sets, analysis models, algorithms and conventions are following the Oncology study protocol CABL001AUS04 version 03.

[figure not shown]
### 1.1 Study design

This study will be a multicenter Phase IIIb open-label, three-cohort study of asciminib in patients with CML-CP without T315I mutation who have had at least 2 prior TKIs and CML- CP harboring the T315I mutation with at least 1 prior TKI (Figure 1-1). Approximately 115 patients will be enrolled in the study. 90 patients without T315I mutation will be randomly selected in Cohort A & B (45 patients per Cohort). Remaining 25 patients with T315I mutation will be enrolled in Cohort C.

The study will contain following Cohorts:

- Cohort A (45): where patients will receive asciminib at 40 mg twice daily
- Cohort B (45): where patients will receive asciminib at 80 mg once daily
- Cohort C (25): patients harboring the T315I mutation will be treated on the dose of 200 mg twice daily.

**Figure 1-1 Schematic of study design**

For patients without T315I mutation, patients will be selected randomly between Cohort A, where patients will be given asciminib at 40 mg twice daily (BID) and Cohort B, where patients will receive asciminib at 80 mg daily (QD) to minimize selection bias. In Cohort C, patients harboring the T315I mutation will be enrolled and treated on the dose of 200 mg twice daily (BID). The higher dose required for that patient population is related to its required concentration to attain optimal blockade of the kinase activity. Patients will continue therapy until disease progression, unacceptable toxicity, or elective treatment discontinuation.

AEs, SAEs, and laboratory evaluation for 24 weeks is the primary endpoint in this study. AEs, SAEs and laboratory evaluation for Cohort A, B and Cohort C, during 48, 72 weeks is the secondary safety endpoint.

The primary analysis will be performed after all patients have been followed for at least 24 weeks or have discontinued study earlier. The end of study medication analysis will be performed after all patients have been followed for at least 72 weeks or have discontinued study earlier. The PFS/OS update analysis will be performed during 24, 48 and 72 weeks of the last patient received the first study dose.

No formal interim efficacy analysis is planned in this study. As the primary time point is by 24 weeks, the primary analysis will be an interim analysis performed when the last patient completes 24 weeks of treatment or discontinues early. As appropriate, annual interim analyses may be planned for publication or any regulatory purpose. Only summary statistics will be provided.

Final Analysis will be performed when the last patient completes 72 weeks of treatment or discontinues early.

## 1.2 Study objectives and endpoints

**Table 1-1      Objective(s) Endpoint(s)**

Primary Objective(s)	Endpoint(s) for primary objective(s)

• To evaluate safety profile of monotherapy asciminib in CML- CP in 3L and beyond, for Cohorts A and B

	

• AEs, SAEs and laboratory evaluation for 24 Weeks.

Secondary Objective(s)	Endpoint(s) for secondary objective(s)

• To evaluate safety profile of monotherapy asciminib in CML- CP in 3L and beyond, for Cohort C

• To evaluate safety profile of monotherapy asciminib in CML- CP in all Cohorts A, B and C

• To estimate the rate of patients with hematologic and molecular response by specific time points for Cohort A, B and C

• To estimate the rate of patients with deep molecular response by specific time points for Cohort A, B and C

• To estimate time to hematologic and molecular response

• To evaluate the duration of hematologic and molecular response

• To Evaluate the progression free survival (PFS)

• To Evaluate Overall Survival (OS)

	

• AEs, SAEs and laboratory evaluation for Cohort A, Cohort B and Cohort C, during 48, 72 weeks

• Rate of CHR, MR2, MMR, by 12, 24, 48, 72 weeks of therapy

• Rate of MR4, MR4.5 by 48, 72 weeks of therapy

• Time to CHR, MR2, MMR, MR4, MR4.5

• Duration of CHR, MR2, MMR, MR4 and MR4.5

• PFS during 24, 48 and 72 weeks

• OS during 24, 48 and 72 weeks

## 2 Statistical methods

### 2.1 Data analysis general information

All analysis will be performed by Novartis.

It is planned that the data from all centers that participate in this protocol will be used for analysis. Analysis datasets and statistical outputs will be produced using the most recent SAS® Version 9.4 (SAS Institute Inc., Cary, NC, USA) or higher, and stored in Novartis global programming & statistical environment (GPS).

There is no formal planned interim analysis.

### Data included in the analyses

The analysis data cut-off dates for the planned analyses are:

- Primary analysis: After random allocation of all patients in their respective Cohort, have been on study medication for 24 weeks or discontinued earlier, i.e., LPFT + 24 weeks.
- Final safety, efficacy [REDACTED] analyses: 30 days after all patients have been on treatment for at least 72 weeks or discontinued earlier, i.e., LPFT + 72 weeks + 30 days. (Note: After the study medication period, the assigned study medication will be made available, may be outside of this study, to patients who in the opinion of the investigators are still deriving clinical benefit.)

All statistical analyses will be performed using all data collected in the database up to the respective data cut-off date. All data with an assessment date or event start date (e.g., vital sign assessment date or start date of an adverse event) prior to or on the cut-off date will be included in the analysis. Any data collected beyond the cut-off date will not be included in the analysis and will not be used for any derivations.

All events with start date before or on the respective cut-off date and end date after the respective cut-off date will be reported as ongoing. The same rule will be applied to events starting before or on the respective cut-off date and not having documented end date. This approach applies, in particular, to adverse event and concomitant medication reports. For these events, the end date will not be imputed and therefore will not appear in the listings.

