Study visits from Week 2 Day 1 will have an allowed “visit window” of +/- 2 day for Week 2 Day 1. Study visits from Week 4 to Week 72 (EOT) will have an allowed “visit window” of +/- 7 days.

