8.1.4 Visit Windows

Study visits from Week 1 Day 1 to Week 2 Day 1 should be completed on the designated date [with an allowed “visit window” of +/- 2 day for Week 1 Day 1 and Week 2 Day 1]. All visits up until Week 4 day 1 need to be performed live by the treating physician on the site.

Study visits from Week 4 to Week 72 (EOT) should be completed every 4 weeks on the designated date [with an allowed “visit window” of +/- 7 days]. After Week 4 day 1, remote visits can be performed using tele-medicine approach with the exception of visits on Weeks 12, 24, 36, 48 and 72.

A delayed visit will have no impact on the next planned visit. The next visit should be completed as scheduled in order to avoid accumulation of additional weeks.

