8.3.1 Laboratory Evaluations

Central laboratory will be used for analysis of hematology and clinical chemistry as specified in the visit schedules in [Table 8-1](#) and [Table 8-6](#) . Details on the collections, shipment of the samples and reporting of results by the central laboratory are provided to investigators in the [\[CABL001AUS04 Laboratory Manual\]](#). The time windows granted for laboratory evaluations are identical with the corresponding visit time windows for each visit.

Local laboratory analysis are allowed only if there is a clinical suspicion of abnormal laboratory values which is supported by a reported adverse event.

When abnormal laboratory values or test results constitute an adverse event (i.e. induces clinical signs/symptoms or requires therapy) they must be recorded on the Adverse Events eCRF. Abnormal laboratory values or test results constitute adverse events only if they induce clinical signs or symptoms, are considered clinically significant (e.g. cause study discontinuation or constitutes in and of itself a Serious Adverse Event) or require therapy (e.g., any hematologic abnormality that requires transfusion or cytokine treatment); and should be recorded on the Adverse Events eCRF under the signs, symptoms or diagnosis associated with them. Refer to the visit schedule for the collection frequency.

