9.2 Study completion and post-study treatment

The patients are treated in the study up to end of study treatment period defined as up to 72 weeks after the last patient receives the first dose unless patients have discontinued treatment earlier. The end of the study will occur when the last patient enrolled (40 mg BID, 80 mg QD or 200 mg BID cohort) into the study completes 72 weeks of treatment or experience treatment failure.

The primary analysis (cut-off date) is defined as the date when all patients (in Cohort A, B and C) have been on study treatment for 24 weeks ([Section 12](#)) or discontinued earlier. Subsequent to this analysis, the primary clinical study report (CSR) will be developed. Following the cut-off date for the primary CSR, the study will remain open. Patients who are ongoing at the time of the primary analysis will continue to receive the study treatments (asciminib) during the study treatment period as defined above. The end of study treatment analysis will be conducted with a cut-off date 30 days after the end of study treatment period to ensure all available treatment data from all patients in the study is analyzed and summarized in a final CSR.

After the end of the study treatment period the assigned study treatment will be made available to patients who in the opinion of the Investigators are still deriving clinical benefit. This may be outside of this study through alternative options including, but not limited to, an expanded access/compassionate use /managed access program or access to commercial supplies in applicable countries.

10 Safety monitoring and reporting

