### On-treatment assessment/event and observation periods

For adverse event, reporting the overall observation period will be divided into two mutually exclusive segments:

- **Pre-treatment period:** from day of patient's informed consent to the day before first administration of study medication
- **On-treatment period:** from date of first administration of study medication to 30 days after date of last actual administration of any study medication (including start and stop date).

**Note:** Patients will be treated for up to LPFT + 72 weeks. This will be the last actual administration of study medication for each patient if the patient has not discontinued study medication earlier. After this period, the assigned study medication will be made available, may be outside of this study, to patients who in the opinion of the investigators are still deriving clinical benefit.

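### The primary data cut-off falls on the last patient's Week 24 target day, so compliant Week 24 assessments done 1 to 7 days late can miss the primary analysis

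*SAP*

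**What the plan says.** SAP Section 2.1 (Data included in the analyses) places the primary cut-off when all patients "have been on study medication for 24 weeks or discontinued earlier, i.e., LPFT + 24 weeks". LPFT is not spelled out; I read it as last patient, first treatment. The same section is strict about later data: "Any data collected beyond the cut-off date will not be included in the analysis and will not be used for any derivations". Protocol 9.2 defines the primary cut-off in the same terms and adds no allowance for visit timing.

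Protocol 8.1.4 says "Study visits from Week 4 to Week 72 (EOT) should be completed every 4 weeks on the designated date", with 7 days allowed either side. The note under Table 8-1 repeats this: "Study visits from Week 4 to Week 72 (EOT) will have an allowed “visit window” of +/- 7 days". Protocol 8.3.1 applies it to blood tests: "The time windows granted for laboratory evaluations are identical with the corresponding visit time windows for each visit". SAP Tables 2-1 and 2-2 set the Week 24 target at Day 169 and accept Days 128 to 211 for molecular and hematologic response.

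For the end of the study, the SAP places the final cut-off when all patients have had at least 72 weeks of treatment "or discontinued earlier, i.e., LPFT + 72 weeks + 30 days". Its on-treatment period runs "from date of first administration of study medication to 30 days after date of last actual administration of any study medication". Protocol 9.2 gives the purpose of the final cut-off: "to ensure all available treatment data from all patients in the study is analyzed and summarized in a final CSR".

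**The concern.** A cut-off on the target day of a visit leaves no room for the late half of that visit's window. A site can see one of the last patients on a permitted day and still have the Week 24 data excluded from the analysis whose time point is Week 24. The same delay in a patient enrolled earlier costs nothing, because that visit falls before the calendar cut-off. Inclusion would then depend on enrolment date and not on compliance.

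The stakes differ by assessment. SAP 2.5 lists laboratory changes, vital signs and notable ECG abnormalities as primary-analysis variables.

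- **Laboratory tests** are also scheduled at Weeks 16 and 20, so little is lost.
- **ECG:** the previous scheduled recording is at Week 12 for Cohorts A and B and also for Cohort C, whose extra ECG is at Week 8 (Protocol 8.3.2.1 and Table 8-2).
- **Vital signs:** Table 8-4 lets them be omitted at Weeks 16 and 20.
- **PCR:** the previous sample is at Week 12 (Protocol Table 8-3). Under SAP 2.8.2 a patient counts as a responder by Week 24 only if the response has been reached at least once by then. A patient whose first response is on the late sample is not a Week 24 responder in the primary report. The same sample, lying within Days 128 to 211, makes that patient a Week 24 responder in a later report.

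**Working it through.** **Inputs.** From the documents: the cut-offs (SAP 2.1), the 7-day visit window (Protocol 8.1.4), the target days (SAP Table 2-1) and the 30-day post-dose period (SAP 2.1.1). My assumptions: Day 1 is the first dose; visit dates are uniform over the 15 permitted days; accrual in the last week of enrolment is 0.4 to 5 patients per week. The SAP tables count Day 1 from random allocation, which I take to be the same day.

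**1. The SAP's target days.** Target day = 7 × week + 1 gives 29, 85, 169, 253, 337 and 505 for Weeks 4, 12, 24, 36, 48 and 72. All six match Table 2-1.

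**2. Primary cut-off for the last-treated patient.**
- LPFT + 24 weeks = Day 1 + 168 = Day 169.
- Permitted Week 24 visit: 169 − 7 to 169 + 7 = Days 162 to 176.
- Excluded: Days 170 to 176, which is 7 of 15 permitted days.
- The Week 24 response window ends 211 − 169 = 42 days after the cut-off.

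**3. Patients treated slightly earlier.** For a patient first dosed k days before LPFT, the cut-off is Day 169 + k, so 7 − k of the 15 days are excluded. For k = 0 to 6 the share is 7/15, 6/15, 5/15, 4/15, 3/15, 2/15 and 1/15. From k = 7 it is zero.

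**4. Expected number affected.** With one patient at k = 0 and r/7 patients per day over the six preceding days:

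expected = 7/15 + (r/7) × (6+5+4+3+2+1)/15 = 0.467 + 0.2r

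patients at risk = 1 + 6r/7

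| Accrual r per week (assumed) | At risk | Expected late | Share of 115 |
|---|---|---|---|
| 0.4 | 1.34 | 0.55 | 0.5% |
| 1 | 1.86 | 0.67 | 0.6% |
| 2 | 2.71 | 0.87 | 0.8% |
| 5 | 5.29 | 1.47 | 1.3% |

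The documents give a rough anchor for this range. Between protocol Amendment 2 (27 January 2021, none enrolled) and Amendment 3 (22 March 2022, 25 enrolled) there are 59.9 weeks, or 0.42 per week. If the primary cut-off fell by 13 January 2023, the date of SAP Amendment 1.0, then LPFT was no later than 29 July 2022. The remaining 90 patients over those 18.4 weeks give 4.9 per week. That cut-off date is itself an assumption.

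**5. Final cut-off.**
- LPFT + 72 weeks + 30 days = 1 + 504 + 30 = Day 535.
- Latest permitted Week 72 visit: 505 + 7 = Day 512, which is 23 days inside the cut-off. No Week 72 assessment is excluded.
- Last dose on Day 505: 505 + 30 = Day 535, so 0 days lost.
- Last dose on Day 512: 512 + 30 = Day 542, so 7 days beyond the cut-off.

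Protocol 6.1.6 and 9.2 and the note in SAP 2.1.1 end treatment no later than LPFT + 72 weeks, which is Day 505 for the last patient. Protocol Table 8-2 times the Week 72 ECG 30 minutes after a dose, at a visit that may be held on Day 512. These statements do not fit together.

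**The case against.** The strongest reply is that the primary endpoint covers safety during 24 weeks of therapy, and a Day 169 cut-off spans those 24 weeks. Adverse events are collected continuously, so none within the period is lost. The main laboratory summaries use the worst on-treatment grade and shifts to it. With results through Week 20 retained, a late Week 24 value matters only if it is the patient's new worst. A late assessment is postponed and not lost, since it falls well before the final cut-off. The response rates are secondary endpoints, and no hypothesis test depends on any of them. All of this stands, and it limits the size of the problem. It does not remove the mismatch: ECG, vital signs and PCR have no equally close earlier assessment, and the SAP's own Week 24 response window runs past its cut-off.

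A reader might go further and infer that adverse events in the last 7 days of the 30-day post-dose period are missing from the final analysis. The documents do not support that. They cap treatment at LPFT + 72 weeks, and under the cap the 30-day period closes on the cut-off day. The Week 72 ECG timing raises a conflict to settle, not an established under-count. Nor does the visit window remove post-dose adverse-event time from the primary analysis, because patients still on treatment at Week 24 have no post-dose period yet.

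**Conclusion.** The point holds for the primary analysis and is minor. A compliant Week 24 assessment done 1 to 7 days late, in a patient first dosed within 6 days of LPFT, is excluded from the primary analysis and deferred. About 0.5 to 1.5 patients are expected to be affected (0.5% to 1.3% of 115), resting on assumed accrual and uniform visit timing. If most visits fall on the designated date, the number is lower. Where a first response is on the deferred PCR sample, one patient is 1/45 = 2.2 percentage points of the Week 24 rate in Cohort A or B and 1/25 = 4.0 points in Cohort C. Those figures do not apply to the worst-grade laboratory tables.

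For the final analysis, the documents show only an inconsistency between the Week 72 ECG timing and the treatment cap.

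**What to change.** Set the primary cut-off at LPFT + 24 weeks + 7 days in SAP 2.1 and in protocol 9.2. Day 176 then covers every permitted Week 24 visit. The cost is a wording change in both documents and a primary cut one week later; no new data are collected.

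The SAP's document history places Amendment 1.0 (13 January 2023) before the primary lock and Amendment 2.0 (15 February 2024) before an interim lock. This suggests, without stating it, that the primary cut has been made. If so, the report can instead give the number of Week 24 assessments dated in the 7 days after the cut-off.

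Separately, reconcile protocol 6.1.6, 9.2 and Table 8-2 with SAP 2.1.1 on when the last dose can fall. Then confirm that the final cut-off covers the last actual dose plus 30 days, and move it only if it does not.
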